5.5.5 Permitted dose adjustments and interruptions of study treatment

Every attempt should be made to maintain patients on the target LCZ696 dose level of 200 mg bid throughout the trial.

If in the opinion of the investigator, the patient does not tolerate the target dose of 200 mg LCZ696 bid (dose level 3), the investigator should consider the following:

1. whether non-disease-modifying medication (e.g., CCBs, diuretics, nitrates, α -blockers) can be reduced to rectify the situation, before reducing the dose of the study drug to a lower dose level (100 mg bid or 50 mg bid LCZ696).
2. may adjust doses of disease-modifying medications (e.g., β -blockers, aldosterone antagonists) if it is believed that they are the most likely cause of the adverse effect.

3. If adjustment/elimination of concomitant medications is not possible or does not alleviate the side effects of concern, the investigator may down-titrate the dose of the LCZ696 to:

- a. the next lower level

The patient should be re-challenged with a higher dose when the investigator feels it is appropriate to do so per the directions provided below in this section.

- b. complete withdrawal of the study drug

If the study drug is temporarily discontinued, it should be reintroduced as soon as medically justified in the opinion of the investigator.

If needed, LCZ696 may be discontinued in favor of starting the patient on an ACEI or ARB (minimum of 36 h between last dose LCZ696 and first dose of ACEI; 12 h between last dose LCZ696 and first dose of ARB).

Study drug dose level adjustments should mainly be based on overall safety and tolerability with special focus on:

- a) hyperkalemia ([Appendix 3](#): treatment guidelines for hyperkalemia);
- b) symptomatic hypotension ([Appendix 4](#): guidelines for management of BP);
- c) clinically significant decrease in eGFR/increase in serum creatinine ([Appendix 5](#): guidelines for management of renal dysfunction).

Any changes in the LCZ696 dose level must be recorded on the Dosage Administration Record eCRF and registered in the IRT.

Adjustment of study drug dose level

If despite adjustment of concomitant medications per the guidance provided above does not rectify the situation, the investigator may consider adjusting the dose of LCZ696 according to the following instructions.

If down-titration is necessary, the patient should be down-titrated to the next lower dose level (Table 5-2 below). The patient may continue to receive the lower dose level for a recommended period of 1 to 4 weeks, or longer based on the investigator's judgment, before re-challenging the patient with the next higher dose level. For example, a patient who encounters tolerability problems at the target dose of 200 mg LCZ696 bid (dose level 3), should receive the study drug at dose of 100 mg LCZ696 bid (dose level 2) for 1 to 4 weeks. Then, based on the investigator's judgment, he/she should be re-challenged with up-titration back to dose level 3.

Table 5-2 LCZ696 dispensed during the open-label treatment period

Study visit	Dose level	LCZ696
Dispensed at Visit 2 and all subsequent visits	3 ^a	200 mg bid
Dispensed at Visit 1 and available for any visit after Visit 1	2 ^b	100 mg bid
Dispensed at Visit 1 for patients that tolerated only dose level 1 in PARADIGM and available for any visit after Visit 1	1 ^c	50 mg bid

a. This dose level should be maintained for as long a duration as possible. If down-titration is necessary due to side effects, the patient should be re-challenged as soon as medically possible per the investigator's judgment.

b. Only if dose level 3 is not tolerated despite modification of other non-disease-modifying HF medications.

c. Only if dose levels 2 and 3 are not tolerated despite modification of other non-disease-modifying HF medications.

If the tolerability issues are not alleviated despite down-titration by one dose level, the investigator may lower the study drug dose further to the next lower level for 1 to 4 weeks, up to temporary or permanent withdrawal of the study drug. Again, once stable, the patient should be re-challenged with up-titration to the next higher dose level every 1 to 4 weeks in an attempt to bring back the patient gradually to the target study drug dose level (dose level 3).

The investigator may choose the next dose level for down- or up-titration according to his or her judgment (Table 5-2). As discussed in [Section 5.5.5](#), the IRT should be contacted to register any changes in the patient's LCZ696 dose level, including cases of temporary and permanent withdrawal of the study drug, and to obtain the medication numbers of the LCZ696 supplies required for the new dose level.

In some instances, according to the safety and tolerability criteria and the investigator's judgment, LCZ696 dose level 1 or 2 can be maintained if he/she considers that the patient's condition would not allow any further up-titration to the target dose of study medication (level 3). In this case it would be acceptable to maintain the patient at dose level 1 or level 2, whichever is the higher and tolerated dose level for the patient.

Study drug restart after temporary treatment interruption

LCZ696 should be reintroduced in those who temporarily discontinue it as soon as medically justified in the opinion of the investigator.

Once the investigator considers the patient's condition appropriate for receiving LCZ696, the investigator should re-start the patient on the study drug at the most appropriate and allowable dose level (Table 5-2) per his/her medical judgment. If tolerated, the patient should be up-titrated up-to dose level 3 every 1 to 4 weeks, as per the investigator's judgment.

Should the patient not tolerate the re-started study drug at a particular dose level, he/she may be down-titrated again (if appropriate) or the study medication discontinued again and a new attempt to up-titrate or reintroduce the study drug could be considered by the investigator if justified in his/her medical judgment.

Study visits should occur as close as possible to the time points indicated in the Assessment Schedule ([Table 6-1](#)). The time interval between the regular visits should be maintained as

scheduled, irrespective of the number of unscheduled visits that may be performed in between, according to the visit and time schedule described in [Table 6-1](#).

Any changes in the study drug dose level, including temporary/permanent withdrawal or restart of the study drug, must be recorded on the Dosage Administration Record eCRF and registered in the IRT.

In case of pregnancy discovered during the open-label treatment period, the patient should be instructed to stop taking the study drug immediately.

See [Section 7.6](#) for further details on pregnancies and reporting guidelines.

5.5.6 Rescue medication

Guidance on handling hyperkalemia, hypotension, and renal dysfunction are provided to investigators in [Appendix 3](#), [Appendix 4](#) and [Appendix 5](#), respectively. Patients may receive open-label ACEIs and/or ARBs during the study **ONLY** if LCZ696 has been discontinued. Resuming ACEI therapy requires a 36 h washout from the last LCZ696 dose.

5.5.7 Concomitant treatment

The investigator should instruct the patient to notify the study site staff of any changes in concomitant medications (new medications or changes in dose regimens of existing medications). All concomitant medications for heart failure must be listed on the Heart Failure Medications eCRF.

5.5.7.1 Heart failure medications and other cardiovascular medications

Patients should be on an optimal medical regimen of background HF medications. The use of an aldosterone antagonist and a β -blocker should be considered in patients eligible for this study. In self-identified black patients, the use of isosorbide dinitrate/hydralazine hydrochloride (e.g., BiDil[®]) should be considered. Every effort should be made to keep the dose level of these background HF medications stable throughout the entire study. However, if the patient's condition warrants a change in any of these medications (for example, if the investigator believes a medication is causing an adverse event), it is allowed at the discretion of the study investigator.

Diuretics may be used and may be adjusted throughout the length of the study at the discretion of the investigator.

5.5.7.2 Medications known to raise potassium levels

Potassium-sparing diuretics, potassium supplements, aldosterone antagonists, and any other medications known to raise potassium levels should be used with caution while the patient is receiving the study medication due to the increased possibility of occurrence of hyperkalemia. The investigator is encouraged to assess patients' potassium levels regularly, especially in those who are receiving these medications.

5.5.7.3 Phosphodiesterase-5 (PDE-5) inhibitors

PDE-5 inhibitors (e.g., sildenafil, vardenafil and tadalafil) should be used with caution while the patient is receiving study medication due to the increased possibility of occurrence of hypotension.

5.5.7.4 Intravenous neseritide, nitroprusside and nitrates

The concomitant administration of LCZ696 with intravenous (i.v.) nitrates has been studied in healthy volunteers. There was no significant difference in the magnitude, dose or time-course of the decrease in systolic and diastolic blood pressure when nitroglycerin was given alone compared to the co-administration of nitroglycerin and LCZ696.

In these healthy volunteers, the administration of LCZ696 and nitroglycerin was safe and well tolerated when given alone or in combination.

The concomitant administration of LCZ696 with i.v. neseritide or nitroprusside has not been studied. In the event a study patient requires the concomitant administration of neseritide and/or nitroprusside with LCZ696, the investigator should consider starting them at a lower dose or a slower infusion rate while monitoring the patient's blood pressure carefully.

The investigator should instruct the patient to notify the study site about any new medications he/she takes after the patient was enrolled into the study. All medications, procedures and significant non-drug therapies (including physical therapy and blood transfusions) administered after the patient was enrolled into the study must be recorded in the source documents.

5.5.7.5 Atorvastatin and other statins

The concomitant administration of LCZ696 and atorvastatin was evaluated in healthy Chinese subjects. At steady state, the levels of atorvastatin increased when co-administered with LCZ696. [REDACTED]

[REDACTED] valsartan levels decreased slightly when administered with atorvastatin. The effect of LCZ696 on other statins has not been examined. Based on these results, caution is recommended when LCZ696 is co-administered with atorvastatin or other statins that are substrates of the organic anion transporters, OATP1B1 and OATP1B3.

5.5.8 Prohibited treatment

5.5.8.1 ACEIs, ARBs and renin inhibitors

In this clinical trial, patients' pre-study ACEIs/ARBs will be replaced with LCZ696.

The concomitant use of open-label ACEIs or ARBs is strictly prohibited while the patient is receiving LCZ696. If the investigator believes that addition of an ACEI or ARB is necessary, then LCZ696 must be discontinued. In order to safely transition from LCZ696 to an ACEI, a period of 36 hours must transpire between the start of the last dose of LCZ696 and the start of the first dose of the ACEI (this is also true if transitioning from an ACEI to LCZ696). However, if the investigator discontinues LCZ696 and replaces it with an ARB, only 12 hours

must transpire between the start of the last dose of LCZ696 and the start of the first dose of the ARB (i.e., the next regularly scheduled dose).

Concomitant administration of renin inhibitors, such as aliskiren, is also prohibited.

5.5.8.2 Other medications

Bile acid sequestering agents, such as cholestyramine and colestipol are prohibited to avoid interference with study drug absorption.

5.5.9 Discontinuation of study treatment

Permanent discontinuation of LCZ696 constitutes withdrawal from the study. Under these circumstances, the patient should be evaluated at a final study visit but will not undergo assessments thereafter unless additional follow-up is required due to prior occurrence of an adverse event.

The investigator must also notify the IRT of the patient's discontinuation of LCZ696 and record it on the Drug Administration Record of the eCRFs.

The emergence of the following circumstances will require study drug discontinuation:

- Withdrawal of informed consent
- Pregnancy ([Section 6.5.6](#) and [Section 7.6](#))
- Investigator thinks that continuation would be detrimental to the patient's well-being

Study medication may be discontinued at the investigator's discretion if any of the following occurs:

- Any severe suspected drug-related AE
- Suspected occurrence of angioedema. A patient with any signs or symptoms of clinically significant angioedema should be thoroughly evaluated by the investigator and constitute a reason for discontinuation of study medication.

Depending on the serum potassium, blood pressure, or eGFR, patients may need to have their LCZ696 dose or the dose of another concomitant medication reduced or discontinued, or, if appropriate, have potentially contributing agents adjusted. Please refer to [Appendix 3](#), [Appendix 4](#) and [Appendix 5](#) for treatment guidelines for hyperkalemia, hypotension, or renal dysfunction, respectively.

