4.2 Exclusion criteria

1. Use of other investigational drugs at the time of enrollment, or within 30 days or 5 half-lives of enrollment, whichever is longer

2. History of hypersensitivity or allergy to any of the study drugs, drugs of similar chemical classes, ACEIs, ARBs, or NEP inhibitors as well as known or suspected contraindications to LCZ696
3. Known history of **angioedema**
4. Requirement of simultaneous treatment with both ACEIs and ARBs
5. Current acute decompensated HF (exacerbation of chronic HF manifested by signs and symptoms) that may require intravenous therapy
6. Symptomatic hypotension and/or a SBP < 100 mmHg at Visit 1 (screening)
7. Estimated GFR < 30 mL/min/1.73m² as measured by the simplified MDRD formula at Visit 1 (screening)
8. Presence of bilateral renal artery stenosis
9. Serum potassium > 5.2 mmol/L at Visit 1 (screening)
10. Evidence of hepatic disease as determined by any one of the following: AST or ALT values exceeding 3 x ULN at Visit 1, history of hepatic encephalopathy, history of esophageal varices, or history of porta-caval shunt
11. Pregnant or nursing (lactating) women, where pregnancy is defined as the state of a female after conception and until the termination of gestation, confirmed by a positive hCG laboratory test
12. Women of child-bearing potential, defined as all women physiologically capable of becoming pregnant, unless they are using **highly effective** methods of contraception during dosing and for **7 days after discontinuation of LCZ696 treatment**.

Highly effective contraception methods include:

- Total abstinence (when this is in line with the preferred and usual lifestyle of the subject).
 - Periodic abstinence (e.g., calendar, ovulation, symptothermal, post-ovulation methods) and withdrawal **are not acceptable methods** of contraception;
- Male sterilization (at least 6 months prior to Visit 1). For female subjects on the study, the vasectomized male partner should be the sole partner for that subject;
[For the United Kingdom ONLY: Male sterilization (at least 6 months prior to Visit 1): Prior to starting dosing of the female subject, medical assessment of the surgical success of the partner's vasectomy must be provided.]
- Combination of any two of the following (a+b or a+c, or b+c):

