 - a. use of oral, injected or implanted hormonal methods of contraception (combined estrogen and progestogen or progestogen only) or other forms of hormonal contraception that have comparable efficacy (failure rate <1%), for example hormone vaginal ring or transdermal hormone contraception.
 - b. placement of an intrauterine device (IUD) or intrauterine system (IUS)
 - c. barrier methods of contraception: condom or occlusive cap (diaphragm or cervical/vault caps) with spermicidal foam/gel/film/cream/vaginal suppository
- In case of use of oral contraception women should have been stable on the same pill for a minimum of 3 months before taking study treatment.

- Women are considered post-menopausal and not of child bearing potential if they have had 12 months of natural (spontaneous) amenorrhea with an appropriate clinical profile (e.g. age appropriate, history of vasomotor symptoms) or six months of spontaneous amenorrhea with the appropriate hormonal profile, or have had surgical bilateral oophorectomy (with or without hysterectomy) at least six weeks prior to study treatment administration. In the case of oophorectomy alone, only when the reproductive status of the woman has been confirmed by follow up hormone level assessment she is considered not of child bearing potential.

13. Any condition, not identified in the protocol that in the opinion of the investigator is likely to prevent the patient from safely tolerating LCZ696 or complying with the requirements of the study.

If a patient has experienced a significant cardiovascular (e.g., acute coronary syndromes, stroke, transient ischemic attack) or non-cardiovascular event in the interim between the end of PARADIGM-HF and the start of CLCZ696B2317, the investigator should ensure that the individual is appropriately stable before enrolling them in the open-label study. If there is uncertainty about a patient's eligibility, the investigator should consult the study medical monitor to determine if the individual should be enrolled.

5 Treatment

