7.7 Reporting angioedema events

It is important that the investigator pays special attention to any swelling or edema that may resemble angioedema that may be reported by patients. If such an event occurs, the investigator will complete a Questionnaire for an Angioedema Event form (provided by the Sponsor in the eCRFs) to summarize the event, its treatment, and its ultimate outcome and communicate this report to the Sponsor as soon as possible. Follow up reports must be communicated to the Sponsor as soon as new information regarding the event becomes available. All hospital records related to the event must be communicated to the Sponsor.

Occasionally, the investigator may be contacted by the Sponsor regarding AEs that were reported on behalf of patients that may resemble an angioedema event. The investigator or his/her delegated staff must complete the required report forms and supply the required

medical records for such events, regardless of whether the investigator views the event in question as angioedema or not.

All angioedema reports will be forwarded to an angioedema adjudication committee by the Sponsor for assessment.

Submission of an angioedema report is not a substitution for the submission of an SAE report. If an angioedema event satisfies the definition of an SAE, the investigator must submit an SAE report (as described in [Section 7.2.2](#)) in addition to the Adjudication Questionnaire for an Angioedema Event.

8 Data review and database management

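### Clinically significant angioedema is a discretionary rather than a required stop, and LCZ696 may be reintroduced afterwards with no angioedema exception, although known angioedema bars entry

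*Protocol*

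**What the plan says.** **Stopping.** Protocol Section 5.5.9 has two lists. The first names what requires discontinuation: withdrawal of consent, pregnancy, and the investigator's view that continuing would harm the patient. The second opens "Study medication may be discontinued at the investigator's discretion if any of the following occurs" and holds two items, severe suspected drug-related events and suspected angioedema. The angioedema bullet then asks for thorough evaluation of clinically significant signs or symptoms and says that these "constitute a reason for discontinuation of study medication".

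**Restarting.** Section 5.5.5 gives the rule twice. In the dose-adjustment steps: "If the study drug is temporarily discontinued, it should be reintroduced as soon as medically justified in the opinion of the investigator". In the later text on restart after interruption: "LCZ696 should be reintroduced in those who temporarily discontinue it as soon as medically justified in the opinion of the investigator". Neither place mentions angioedema.

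**Entry.** Exclusion criterion 3 in Section 4.2 is "Known history of angioedema".

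**Potassium.** Under Appendix 3, a value of 6.0 mmol/L or above means an immediate stop, notice to the sponsor within 48 hours, and no restart until the case has been discussed with the Medical Monitor, who must agree.

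**Adjudication.** Section 7.7 requires forms and records for events that resemble angioedema, "regardless of whether the investigator views the event in question as angioedema or not". It adds: "All angioedema reports will be forwarded to an angioedema adjudication committee by the Sponsor for assessment". Section 8.5 repeats the forwarding step. Neither section says who receives the committee's assessment. SAP Section 9.7.1.6.1 counts angioedema and angioedema-like events descriptively and does not mention adjudication results.

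**The concern.** The protocol treats angioedema as important enough to bar entry and to have its own questionnaire and committee. Once a patient is on LCZ696, however, a clinically significant episode does not compel a stop under the list in which it sits. If the investigator chooses a temporary interruption, the general restart rule applies unchanged.

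Sites could therefore read the same bullet in two ways: as a near-instruction to stop, or as one factor in a discretionary decision. A site taking the second reading could re-expose a patient to LCZ696 after a clinically significant episode without breaching the protocol, and without any required discussion with the sponsor's Medical Monitor. What is at stake is the safety of a small number of patients. No hypothesis test or sample size is affected, because the study has one arm and plans no treatment comparison (Protocol Section 9.7).

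**Working it through.** No formula applies to the core of this point, so the check sets the rules side by side.

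| Situation | Stop | Restart | Source |
|---|---|---|---|
| Known angioedema before entry | Patient not enrolled | Not applicable | Protocol 4.2, criterion 3 |
| Clinically significant angioedema on study | Discretionary list, though called a reason to stop | Investigator's opinion; no exception | Protocol 5.5.9, 5.5.5 |
| Potassium of 6.0 mmol/L or above | Immediate | Medical Monitor must agree | Protocol Appendix 3 |

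1. *Is the stop required?* Angioedema is absent from the required list in 5.5.9. The nearest required item, that continuing would be detrimental, is also the investigator's judgement. The sentence on clinically significant cases leans towards stopping, but its bullet is governed by the permissive opening line.

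2. *Is restart restricted?* Both statements of the rule in 5.5.5 turn on medical justification in the investigator's opinion. Section 7.7 deals with reporting and says nothing on dosing. No other text in either document restricts restart after angioedema.

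3. *Does the protocol show that a restriction is practicable?* Yes. Appendix 3 already uses a stop, a notification and a permission step for one other safety event.

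4. *Scale.* The documents give no angioedema rate. For workload only, each 0.1% of the planned 5,000 patients with an event is 5,000 × 0.001 = 5 patients. This is a unit of scale and not an estimate.

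**The case against.** The strongest reply is that clinically significant angioedema is already largely handled. The bullet calls for thorough evaluation and names the event as a reason to stop. Drug must be stopped if continuing would be detrimental, and it returns only when medically justified. A reader might infer that 5.5.5 orders re-challenge after angioedema, but the medical-justification condition rules that out. The reply shows that a careful investigator would probably stop. It does not remove the conflict inside 5.5.9 or supply the missing exception in 5.5.5.

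A second reply is that entry limits and on-study rules differ by design. Potassium above 5.2 mmol/L excludes a patient, yet a value above 5.3 and up to 5.5 on study leads to review and monitoring, with down-titration only considered. An eGFR below 30 excludes, yet Appendix 5 leaves a renal stop to the investigator. This is true, but those are laboratory values that can recover, whereas a history of angioedema remains. The reply does limit the comparison. A reader might infer that the protocol is stricter on safety generally. The one real comparator is potassium of 6.0 mmol/L or above. The medical monitor's role in eligibility doubt ("the investigator should consult the study medical monitor to determine if the individual should be enrolled") concerns enrolment, and the renal rule asks only for notice when drug is stopped.

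A third reply concerns the committee. The sponsor receives every angioedema report, already contacts sites about possible events, and may have a charter that returns the assessment. Silence in Sections 7.7 and 8.5 therefore does not show that results are withheld from sites. That stands, and it makes the return route a secondary clarification.

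Finally, the proposed rule still depends on the investigator judging what is clinically significant. That also stands. The change fixes what follows from the judgement, not who makes it.

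**Conclusion.** The point holds as a cheap safety improvement. The stop for clinically significant angioedema is worded permissively and ambiguously, and the restart rule lacks an exception that the entry criteria and the potassium rule would lead one to expect. The number of patients affected is unknown and probably small.

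Two stronger readings are not supported. A reader might infer that a patient whose event the committee confirms against the investigator's view would have been barred from entry. Criterion 3 needs a known history, and an event that the investigator did not regard as angioedema might not have counted as known. A reader might also infer that the sponsor is left unaware; Section 7.7 requires reports as soon as possible, and serious events also need an SAE report.

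The conclusion assumes that sites follow the protocol text as written, and that no document outside the two reviewed overrides 5.5.9 or 5.5.5 for angioedema.

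**What to change.** 1. **Section 5.5.9.** Move clinically significant angioedema to the list that requires discontinuation. Leave merely suspected cases in the discretionary list.
2. **Section 5.5.5.** Add: *LCZ696 is not given again after clinically significant angioedema. After any other confirmed angioedema, restart needs prior discussion with the Sponsor's Medical Monitor, and his or her permission.* The potassium rule in Appendix 3 is the model.
3. **Sections 7.7 and 8.5 (secondary).** Add: *The committee's assessment of each report is sent promptly to the investigator and the Medical Monitor.* If a charter already says this, a cross-reference is enough.

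The changes need no new data, committee or analysis. The drafting is short, but the text must go through a protocol amendment, with sponsor, ethics and, where required, health-authority approval (Section 11.1). The running cost is a few case reviews: at most 5 for each 0.1% of 5,000 patients with an event. A few patients would also leave the study, because 5.5.9 treats permanent discontinuation as withdrawal; they would have a final visit, and further follow-up only where an adverse event calls for it.
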